9.3.3. Reporting of Pregnancy

Although not AEs, pregnancies are reportable events. Any pregnancies that occur during the study period in women who have received any study product (fluconazole or placebo) will be reported via the AdvantageEDC on the Pregnancy Report form within 5 days of site awareness. The report will include pregnancy outcome (e.g., any premature terminations, elective or therapeutic, any spontaneous abortions or stillbirths), as well as the health status of the mother and child, including date of delivery and infant’s sex and weight. Pregnancies will be followed up to two months after birth. All pregnancies will be reported to the clinical data management group. If the database is locked at time of pregnancy, a supplemental report will be generated and completed after birth and follow-up, which will be appended to the database.

9.4. Type and Duration of Follow-up of Subjects after Adverse Events

SAEs will be followed from the time of enrollment until completion of study even if this extends beyond the study-reporting period. For those subjects who are dismissed from study follow-up after study Day 43 (Visit 04), SAEs will be followed but new SAEs will not be collected. All subjects who received fluconazole will be followed through Day 49. Resolution of an SAE is defined as the return to pretreatment status or stabilization of the condition with the expectation that it will remain chronic.

Follow-up procedures, evaluations, and outcomes will be recorded on the appropriate data collection form.

9.5. Halting Rules

For all subjects:

- A. If more than 10% (and at least 5) of randomized subjects develop clinically significant elevations in liver enzymes as defined below, study enrollment will be halted for DSMB review.
 - If any of the following criteria for liver-related adverse events are met and confirmed:
 - AST elevation of >5X ULN or greater than or equal to 225 IU/L or
 - ALT elevation of >5X ULN or greater than or equal to 250 IU/L or

-
- Total bilirubin elevation >1.5X ULN or
 - Aminotransferase elevation of >3X ULN accompanied by total bilirubin elevation >1.5X ULN
- B. If more than 1% (and at least 2) of the randomized subjects develop QT prolongation or clinical symptoms indicative of symptomatic QT prolongation as defined below, study enrollment will be halted for DSMB review.
- QTc prolongation > 500ms or >60ms above baseline measurement
 - Torsades de pointes (torsades, TdP)
 - Cardiac Sudden death
 - Unexplained Syncope
 - Seizure in non-epileptic patients

The DSMB will review the study for efficacy according to the interim analysis plan.

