5.3. Treatment Assignment Procedures

5.3.1. Randomization Procedures

Per International Conference on Harmonisation (ICH) guideline E6: Good Clinical Practice (GCP), screening records will be kept at each participating site to document the reason why an individual was screened, but failed trial entry criteria. The reasons why individuals failed

screening will be recorded in the Statistical and Data Coordinating Center's (SDCC) AdvantageEDCSM (Electronic Data Capture System).

Using a centralized randomization system, eligible subjects will be randomly assigned to 1 of 2 groups (1:1 ratio) to receive either 42 days of placebo or 400 mg/day fluconazole capsules. The randomization code will be prepared by statisticians at the SDCC and sent to the DMID Clinical Agents Repository where the study product will be labeled with a randomization code which links to the treatment assignment. Once consented and determined to be eligible for the trial, the subject will be assigned the next available assignment in sequence of the product available at the site. The randomization code of the distributed study product will be entered into AdvantageEDC upon enrolling the subject in the trial. Instructions for use of the enrollment module are included in the AdvantageEDC User's Guide.

If emergency unblinding is required, the site may determine the treatment assignment by contacting the SDCC or through AdvantageEDC.

Subjects who sign the informed consent form and are randomized but do not ingest the study drug will be replaced. Subjects who sign the informed consent form, and are randomized, receive the study drug, and subsequently withdraw consent, are withdrawn or terminated from the study, or are lost to follow-up will not be replaced.

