7.3. Follow-up (Days 22-180, Visits 02-07)

7.3.1. Follow-up Visit Visit 02 (Day 22):

(Window: Day 20 to Day 23):

- Interview subjects and review the medical record for interim medical history, including an assessment for new medical conditions and symptoms, hospitalizations, diagnosis of disseminated coccidioidomycosis. Note any changes since the previous clinic visit.
- Perform a urine or serum pregnancy test on all women of childbearing potential. The test must be negative to ensure continued eligibility.
- Review any concomitant medications since previous study visit. Record all concomitant medications on the appropriate data collection form.
- Review of inclusion/exclusion criteria by clinician licensed to make medical diagnoses to determine continued eligibility.

-
- Perform a targeted physical examination if indicated based on review of complete medical history and any updates obtained by interview of subjects since the Day 1 visit by a clinician licensed to make medical diagnoses.
 - Record vital sign measurements (sitting blood pressure, sitting heart rate, respiratory rate, oral temperature, oxygen saturation and weight).
 - Query subject regarding whether the subject has taken their dose for today. If the subject has not yet taken their dose for today, subject should be instructed to take the day's dose in the clinic, prior to the pill count.
 - Perform a pill count of study product (fluconazole or placebo) and interview to determine adherence. Review need to bring pill bottles for count to each visit, study product dosing and storage requirements and ability to meet requirements with subject.
 - Following pill count, collect the pill bottle A and retain until study product accountability has been completed by the study monitor.
 - Note any discrepancies between expected and actual pill count remaining in pill bottle B.
 - Review randomization number assigned at Visit 01 and dispense final bottle (bottle C) of study product. Instruct the subject to continue to take daily doses from pill bottle B and to begin taking their daily doses from the newly dispensed bottle (bottle C) once bottle B is empty.
 - If subject did not return the pill bottle A dispensed at Visit 01, instruct them to return this bottle at their next visit.
 - Complete FLEET CAP Score
 - Collect the number of days missed from school and/or work due to illness for subjects who were either enrolled in school or employed at baseline

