The DSMB will operate under the rules of a DMID-approved charter that will be written at the organizational meeting of the DSMB. At this time, each data element that the DSMB needs to assess will be clearly defined. Procedures for DSMB reviews/meetings will be defined in the charter. The DSMB will review applicable data to include, but not limited to, study progress and participant, clinical, safety, and immunogenicity data which may include enrollment and demographic information, medical history, concomitant medications, physical assessments, clinical laboratory values, dosing, protocol defined SAEs, and assays results. Additional data may be requested by the DSMB, and interim statistical reports may be generated as deemed necessary and appropriate by DMID. The DSMB may receive data in aggregate and presented by group. The DSMB may also be provided with expected and observed rates of the liver function abnormalities in an unblinded fashion. The DSMB will meet and review this data at scheduled time points or ad hoc as needed during the study as defined in the protocol and DSMB charter. As an outcome of each review/meeting, the DSMB will make a recommendation as to the advisability of proceeding with the study (as applicable), and to continue, modify, or terminate the study.

DMID or the DSMB chair may convene the DSMB on an ad hoc basis according to protocol criteria or if there are immediate concerns regarding observations during the course of the study. The DMID Medical Monitor is empowered to stop enrollment and dosing of the study drug if halting criteria are reported. The DMID Medical Monitor will be responsible for reviewing any protocol defined SAEs in real time. The DSMB will review safety events on a regular basis and ad hoc during the study.

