11.3.2. Interim Immunogenicity or Efficacy Review

At the second and third interim analysis, the unblinded statistical team will calculate the probability conditional on the current trend in the accumulated data that the final analysis will show a benefit in favor of fluconazole. The DSMB will report to the sponsor only that the trial met the standard for continuation (conditional power above 5%). The sponsor will weigh the recommendation of the DSMB regarding futility and the separate blinded assessment of enrollment feasibility, and will decide whether to continue the trial, and if so, whether to increase the sample size, and by how much. It is recognized that statistical futility (low conditional power), and operational futility (unachievable enrollment targets), are closely related issues, and that this somewhat arbitrary distinction is being made to facilitate blinded decision making. The power calculations in Section 11.2.1 considered the power of the Z test for a fixed sample size and no interim analysis. A simulation study was performed to calculate the power available for the final analysis in a trial containing a futility analysis to be performed after 500 and 750 subjects have been enrolled and followed until Day 22. In this setting, uniform enrollment was also assumed.

At each futility analysis, the conditional power was calculated and if the conditional power was less than 5%, the trial was terminated. [Table 7](#) displays the power of the Z test for different Day 22 response rates resulting from the simulation study. Comparing these results with [Table 5](#) in

Section 11.2.2., there is minimal impact on power. If the true clinical response proportions are 0.20 and 0.40, the power drops slightly to 85.9%.

Table 7: Power of the Z Test for Different Day 22 Response Rates with a Futility Analysis

		Rate in Fluconazole Arm								
		0.1	0.2	0.3	0.4	0.5	0.6	0.7	0.8	0.9
Rate in Placebo Arm	0.1	4.8	48.7	93.9	99.8	100.0				
	0.2		4.7	34.9	85.9	99.1	100.0			
	0.3			4.7	30.1	80.8	98.6	100.0		
	0.4				5.0	27.7	78.7	98.6	100.0	
	0.5					4.8	28.0	80.5	99.1	100.0
	0.6						5.0	29.6	85.6	99.9
	0.7							4.7	34.8	94.0
	0.8								4.7	49.2
	0.9									4.8

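### Both halting rules in 9.5 pool the two arms, so an excess confined to fluconazole is halved before it is compared with the 10% and 1% limits

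*Combined protocol and SAP*

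**What the plan says.** Section 9.5 introduces its rules with "For all subjects". Rule A (liver) applies "If more than 10% (and at least 5) of randomized subjects develop clinically significant elevations in liver enzymes as defined below". Rule B (cardiac) applies "If more than 1% (and at least 2) of the randomized subjects develop QT prolongation or clinical symptoms indicative of symptomatic QT prolongation". Meeting either rule halts enrollment for DSMB review. Neither rule names an arm, and 5.3.1 states that "eligible subjects will be randomly assigned to 1 of 2 groups (1:1 ratio"), so about half of each denominator is on placebo.

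By-arm review is described separately and as an option. Section 9.6.2 says "The DSMB may receive data in aggregate and presented by group", adds that liver abnormality rates *may* be shown unblinded, and schedules reviews at 250, 500 and 750 enrolled and at least annually. For futility, 11.3.2 already has people who work unblinded: "At the second and third interim analysis, the unblinded statistical team will calculate the probability conditional on the current trend". The first on-treatment safety laboratory is at the Day 22 visit (7.3.1, "Window: Day 20 to Day 23").

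**The concern.** The rules are meant to catch liver and cardiac harm, which the protocol attributes to fluconazole (2.3.1, 9.1). Half of the denominator does not take fluconazole. If the excess arises only on active drug, the pooled percentage is about half the excess in exposed subjects. A fluconazole rate clearly above the stated percentage can then leave the rule unmet.

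What is at stake is the timing of a DSMB review while enrollment continues. Section 2.3.1 says that most enrollees will not have coccidioidomycosis, so most subjects exposed to the drug have no fungal infection for it to treat. Section 9.5 gives no expected rates and no operating characteristics, so a reader cannot see how the rules behave for the fluconazole arm.

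**Working it through.** **Inputs.** From 9.5: T = 10% with a floor of 5 events (rule A), and T = 1% with a floor of 2 (rule B). From 5.3.1: 1:1 allocation. From 11.2.3: 1,000 subjects. From 9.6.2: reviews at 250, 500 and 750. The plan states no figure for these rules, so there is none to reproduce. All true event rates below are assumptions.

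**Step 1: the limit in terms of the fluconazole rate.** Let f and p be the observed fluconazole and placebo rates. The rule is met when (f + p)/2 > T, that is, when f > 2T − p.

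- Rule A: f must exceed 20% at p = 0, 17% at p = 3%, 15% at p = 5%, and 10% at p = 10%.
- Rule B: f must exceed 2.0% at p = 0, 1.5% at p = 0.5%, and 1.0% at p = 1%.

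**Step 2: minimum counts.** The count needed at n randomized is the larger of the floor and int(T·n) + 1. If all events are on fluconazole (n/2 subjects):

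| n | Rule A | Share of arm | Rule B | Share of arm |
|---|---|---|---|---|
| 250 | 26/125 | 20.8% | 3/125 | 2.4% |
| 500 | 51/250 | 20.4% | 6/250 | 2.4% |
| 750 | 76/375 | 20.3% | 8/375 | 2.1% |
| 1,000 | 101/500 | 20.2% | 11/500 | 2.2% |

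At 500 randomized, five rule B events all on fluconazole are 5/250 = 2% of that arm. They are 5/500 = 1% pooled, which is not more than 1%.

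**Step 3: probability that rule A is met at a fixed look.** For the pooled rule this is P(X + Y ≥ k), with X ~ Bin(n/2, f), Y ~ Bin(n/2, p) and k from step 2. For the fluconazole arm alone it is P(X ≥ k′), with k′ = 13 of 125, 26 of 250 or 51 of 500. With true f = 15%:

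| Placebo rate | n = 250 | n = 500 | n = 1,000 |
|---|---|---|---|
| 1%, pooled | 9.5% | 4.0% | 0.8% |
| 3%, pooled | 24% | 19% | 12% |
| 5%, pooled | 45% | 46% | 47% |
| any, fluconazole arm only | 95% | 99% | >99% |

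As a plausibility check at n = 250: the expected pooled count is 125 × 0.15 + 125 × 0.01 = 20.0 at 1% placebo, and 25.0 at 5%, against 26 needed. The expected fluconazole count is 18.75 against 13 needed.

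**Step 4: probability of ever being met over 1,000 subjects.** The protocol does not say how often the rules are checked, so continuous checking is assumed. So is a reporting lag of 12 randomizations (1,000 subjects over 60 months, about 1,826 days, × 21 days ≈ 11.5).

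- Rule A at 15% versus 1%, 3% or 5%: pooled about 40%, 63% or 84%; fluconazole arm about 100% throughout. With no lag, pooled is about 77% at 3% and 92% at 5%.
- Rule B at 1.5% versus 0.1%: pooled about 64%, fluconazole arm about 93%.

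**The case against.** Pooled, blinded halting rules backed by a DSMB that can see data by group are a coherent design. Section 9.5 sets a trial-wide trigger for review; it does not promise fluconazole recipients a 10% or 1% ceiling. Any subject who meets the liver criteria, or most of the cardiac ones, stops study drug individually (5.3.3.1, 9.2.3). DMID or the DSMB chair can convene an ad hoc review at any time (9.6.2). All of this stands, and it limits the point. But individual stopping protects the affected subject, not those still being enrolled, and an ad hoc meeting needs someone to see a concern. Non-serious events are not collected (9.2.1), and SAEs are confined, birth defects aside, to unexpected events suspected to be drug-caused (9.2.2), so known liver or QT effects may not arrive by that route. None of these supplies a by-arm threshold.

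Three stronger readings are tempting and are not supported.

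- *That true toxicity must reach 20% or 2%.* These are observed rates with no placebo events. The criteria include isolated bilirubin rises, syncope and seizure, which can occur on placebo. The small floors also let a rule fire early: 5 liver events among the first 49 randomized, or 2 cardiac events among the first 199.
- *That a fluconazole rate above the limit would usually not halt enrollment.* This is false for rule B at 1.5% versus 0.1% under continuous checking (about 64%), and for rule A at 15% versus 5% (about 84%).
- *That undosed subjects add materially to the dilution.* They are replaced (5.3.5), and the first dose is observed in clinic (7.2).

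**Conclusion.** The point holds as a limited design weakness. Pooling under 1:1 allocation halves an excess confined to fluconazole, and no section sets a by-arm trigger to compensate. The loss is large for rule A when the placebo rate is low and the rule is checked at the scheduled reviews: at 250 randomized, 10% to 45% pooled against 95% by arm, over placebo rates of 1% to 5%. It shrinks as the placebo rate or the frequency of checking rises, and it is moderate for rule B.

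The algebra and minimum counts follow from the protocol. The probabilities rest on assumed true rates, on the assumed checking frequency and lag, and on events being detected. The last matters for rule B, because no routine on-treatment ECG is scheduled (8.1, Table 12). Nothing here bears on whether 10% and 1% are the right clinical limits.

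**What to change.** In 9.5 and the DSMB charter, leave the pooled rules, percentages, minimum counts and event definitions as they are, and make two additions.

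1. The unblinded statistical team of 11.3.2 also evaluates each rule in dosed fluconazole-arm subjects, at a stated frequency. If a rule is met there, it notifies the DSMB only, for an ad hoc review. Telling the sponsor's Medical Monitor that an arm rule is met while the pooled count is below its limit would reveal an imbalance.
2. In 9.6.2 and 11.3.1, by-group safety data *will* be provided to the DSMB, in place of *may*.

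The cost is protocol and charter wording, a recurring unblinded tabulation by a team now described only for the second and third interim analyses, and somewhat more ad hoc reviews. For rule B at 0.2% versus 0.1%, the fluconazole-arm check is met in about 6–7% of trials, against about 4% for the pooled rule. For rule A at 2% versus 1%, the arm check is met in about 0.2%.

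Testing both arms separately, with an automatic halt, would cost more. With no drug effect and 0.5% in each arm, rule B halts would rise from about 32% to 56% of trials; at 6% in each arm, rule A halts would rise from about 13% to 37%. That is why the added check is limited to the fluconazole arm and leads to a review rather than a halt.
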